PROTOCOL TITLE:

High Frequency Oscillation in Pediatric Epilepsy Surgery

Protocol Version Date: 26 Oct 2017

NCT03790280

PROTOCOL TITLE:

High Frequency Oscillation in Pediatric Epilepsy Surgery

Protocol Version Date: 26 Oct 2017

NCT03790280

Principal Investigator:

[name]

UCLA Mattel Children's Hospital
David Geffen School of Medicine at UCLA
Division of Pediatric Neurology
[name]
Los Angeles, California, USA
[contact]
[contact]

Co-Investigators:

[name], MS
[name], PhD
[name], MS
[name]

Study Coordinators:

[name]
[name]
[name]
[name]

Funding:

None

Introduction:

Intra-operative electrocorticography (ECoG), based on interictal spike and spike patterns, is performed to optimize delineation of the epileptogenic tissue in the operating room during epilepsy surgery. Similarly, extra-operative electrocorticography is often recorded over days to weeks with intracranial grids and depth electrodes, when the epileptogenic zone is not clearly localized with non-invasive studies and/or with intra-operative ECoG. Surgical resection following extra-operative ECoG is then "tailored" by the seizure onset zone as the gold standard. High frequency oscillations have been identified as a more precise biomarker for epileptogenic tissue. The aim of the study is to determine prospectively if ECoG- tailored surgery combining HFOs and standard clinical resection with ECoG, compared to standard clinical resection with ECoG alone, is feasible and will lead to an equal or better seizure outcome; the comparison to HFO + ECoG, versus ECoG alone, could be either in the form of interictal spikes on intra-operative ECoG or seizure onset zone on extra-operative ECoG.

Background and Rationale:

Epilepsy occurs in 0.5-0.7% of the population, of which 25% are children. About 30% of subjects with focal epilepsy do not respond well to medication, and half of them are eligible for epilepsy surgery. In recent years, the importance of early epilepsy surgery has been stressed, as successful surgery may lead to seizure- and medication-freedom and improved social and cognitive development, especially in children. The current rate of seizure freedom following epilepsy surgery is around 65%. During surgery, in most medical centers, either intra-operative ECoG is recorded to identify the irritative zone, defined by the spatial distribution of interictal spikes, or extra-operative ECoG is recorded to identify the seizure onset zone. The presence of epileptiform brain activity/spikes, or the seizure onset zone, identified by clinical neurophysiologists, is used to guide the neurosurgeon with respect to the boundaries of brain tissue that is necessary for resection to achieve seizure freedom. Spikes are considered biomarkers of the presence of epilepsy, and seizure onset zone indicates where the seizures may be generated. Neither spikes nor seizure onset zones accurately identify the location and the extent of the epileptogenic zone, defined as the cortical tissue whose complete removal is necessary to achieve post-operative seizure freedom.

High frequency oscillations (HFOs, 80-500 Hz) on ECoG have recently been identified as a new biomarker for epileptogenic tissue. Retrospective observational research, as well as more recent prospective observational studies, show that HFO presence strongly relates to, and may predict more accurately, the epileptogenic zone, and that the resection of brain tissue containing HFO may be superior than resection of brain tissue containing spikes and seizure onset zone in rendering patients seizure-free. The area showing HFOs usually overlaps with, but may be smaller than, the area with spikes

and seizure onset, and HFOs do not tend to propagate to distant sites as spikes and seizures do.

Standard Clinical Practice

During surgery, current clinical practice is to measure epileptic activity that we call epileptic spikes (on intra-operative ECoG) or seizure onset zone (extra-operative ECoG) with EEG recordings. Current clinical standard of practice in either intra-operative ECoG or extra-operative ECoG is recorded to identify epileptic zone and seizure onset zone. The presence of epileptiform brain activity/spikes, or the seizure onset zone, identified by clinical neurophysiologists, is used to guide the neurosurgeon with respect to the boundaries of brain tissue that is necessary for resection to achieve seizure freedom. The particular part of the brain that has either of these abnormalities, is removed. We have used this method for over 40 years.

New Research HFO Method

Recently, it has been discovered that we can also measure other epileptic activity, High Frequency Oscillations or HFOs, by recording EEGs at a higher frequency rate. These HFOs on the EEG recordings appear to point out the epileptic brain tissue better than epileptic spikes or seizure onset zone.

In this study we will compare the two groups of patients to see what works best: standard clinical practice only, or standard clinical practice along with HFOs. The results of this study may change the way we operate on epilepsy surgery patients in the future.

Hypothesis: We hypothesize that the strategy of incorporating HFO data to a standard ECoG-guided resection in pediatric epilepsy surgery will result in improved postoperative seizure outcome than the traditional approach.

Objective:

The primary objective is to determine if HFO data in addition to ECoG data (experimental group, arm 1), compared to standard ECoG data alone (current standard control group, arm 2), will lead to improved post-surgical seizure outcome 1 year after surgery.

Secondary objectives include the comparison of incidence of neurologic deficits, neuropsychological outcomes (when available with clinical testing), and quality of life outcomes.

Study Design and Procedures:

A single-blinded randomized control trial including subjects with refractory focal epilepsy who undergo surgery with intra- or extra-operative electrocorticography. Surgery is

tailored by HFOs and standard ECoG interpretation (spikes on intra-operative ECoG or seizure onset on extra-operative ECoG) (arm 1), or tailored by standard ECoG alone (arm 2).

Randomization

Informed consent will be obtained 1 to 7 days to up to 3 months prior to the day of surgery. Prior to surgery, the subject will be randomized into the cohort arm in a 1:1 ratio.

Blinding

Blinding of the clinical neurophysiologists and neurosurgeons for treatment allocation is not feasible because of the character of the intervention. Therefore, this is a single-blinded trial as subjects will be blinded to the cohort arm to minimize bias of the follow-up results. The treating neurologist, if other than the clinical neurophysiologists in this study, will remain blinded.

Number of Subjects:

30

Inclusion Criteria:

- Age 0-21
- Refractory focal epilepsy
- Planned resective epilepsy neurosurgery with ECoG, with the goal of tailoring the resection

Exclusion Criteria:

- Subjects undergoing non-resective neurosurgery

Recruitment of Subjects:

Subjects with refractory epilepsy undergoing epilepsy surgery with ECoG to guide the extent of the resection.

Length of Study Visits and detail:

This research study will not require any additional time in the hospital after surgery. However, will be following the subject for epilepsy outcome up to 12 months after surgery.

Chart review of clinical records such as neurological, MRI, EEG and other clinically relevant information pertaining to the outcome of surgery will be collected.

Subjects or their caregivers will be asked to fill out questionnaires about seizure frequency, medication and day to day function in various life areas at each visit with the neurosurgeon/neurologist.

Schedule of events below:

PRE-SURGERY	SURGERY	POST-SURGERY				
		Visit 2	Visit 3	Visit 4	Visit 5	Visit 6
0 day-3 months prior to surgery		1-7 days after surgery	3 months	6 months	9 months	12 months

Pre-Surgery

- Consent
- Neurosurgeon visit
- Baseline Questionnaire

Post-Surgery (at every visit)

- Neurosurgery/Neurology Visit
- Follow-up Questionnaires

Questionnaires will take about 30 minutes to complete. We may send the questionnaires home a week prior to a return visit to alleviate time at the doctor's office.

Questionnaires

NIH Pediatric Stroke Scale

Child Behavior Check List

Quality of Life in Epilepsy (Adults)

Quality of Life in Childhood Epilepsy

Procedure Detail:

Intra-operative ECoG, which could be pre-resection, post-resection, or both, during brain surgery would be determined based on clinical decisions. Similarly, extra-operative ECoG would also be determined based on clinical decisions, and would be pre-resection.

For those subjects randomized to the standard clinical care with ECoG only (control arm), ECoG would be recorded but not assessed for HFO until after the clinical decision has been made with respect to site and margin of the resection. Only cortical areas deemed abnormal by standard clinical ECoG would be resected.

For those subjects randomized to the HFO + standard clinical care with ECoG combined (experimental arm), ECoG would be recorded AND assessed for HFO rapidly in the operating room (within 10 minutes) to minimize patient risk and while the neurosurgeon begins the initial resection. Should HFO persist after resection, further resection to ensure complete removal of HFO and standard clinical ECoG abnormalities may be possible. Cortical areas generating HFO and/or abnormal by standard clinical ECoG would be resected, with the exception of HFO-only presence in eloquent cortex, which would be spared. Eloquent cortex is defined as sensorimotor cortex, primary language cortex (Wernicke's and Broca's areas), and primary visual cortex.

Benefits of Study:

HFO analysis could determine/predict a better surgical outcome.

Potential Risks:

In epilepsy surgery there are always risks.

1. The patient may not become seizure free.
2. The patient may lose or may damage an area that is close to important function such as motor or speech functions.
3. The patient may develop a surgical complication such as infection, hydrocephalus or stroke.

In Standard Surgery plus HFO Method Risk: Additional risk may be unexpected neurologic deficit.

There will be every effort made to minimize loss of major brain function, such as language, motor skills, sensation, and vision, to what may be already anticipated from the standard clinical care approach. Should any of these 4 major brain function areas be found to have HFOs only, and not on standard ECoG analysis, these important areas of brain function will not be resected.

The likelihood of longer anesthesia time is very low since HFO analysis will begin before or concurrently with standard method. Therefore we do not expect any additional time under anesthesia for either method.

There is no additional risk of recording HFOs at higher frequencies. Higher frequency simply allows us to capture brain signals at higher frequency rate.

Randomization: There is no risk or benefit from randomization given that standard of care ECoG will be completed during surgery.

Questionnaires: There are no risks to these questionnaires other than the inconvenience of the time involved in answering the questions.

Potential risks include loss of confidentiality. To protect you from this risk, all electronic study data will be kept in a password-protected, encrypted database. Other study related materials that include personal health information will be kept in a secure area accessible only by study personnel.

Where will data be stored?

Data will be stored in an encrypted database which is password protected. Only study personnel will have access to the data. EEGs data done at UCLA, for data analysis will be de-identified. This information will be stored in a secure area accessible to authorized personnel only and data will be kept for future studies and or publication.

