**NCT03790280**

### **Statistical Analysis Plan (SAP):**

Our primary comparisons will be the comparison of post-surgery seizure free-time between the SOC and SOC+HFO study arms. The primary analysis will be a log-rank test. The secondary analysis of the primary endpoint will be a Cox-proportional hazards regression with seizure-free survival time as the outcome. Covariates will be treatment, and subject-level characteristics (ex. age and gender). Secondary outcomes of 2-year seizure-free rate will be assessed with logistic regression models using a similar set of covariates that will be included in the Cox model. Surgical complication rates will be compared using Fisher's exact tests for the overall analysis. The intent-to-treat principal will be utilized and subjects will be included in the randomized study arms for analysis rather than the actual treatment received. We will conduct a secondary analysis based on treatment received.

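### Does an introductory aim of an equal or better seizure outcome oblige the plan to include an equality or non-inferiority analysis?

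*Protocol*

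**What the plan says.** Four places in the protocol say what the comparison is for.

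- Introduction: the question is whether the combined approach "is feasible and will lead to an equal or better seizure outcome".
- New Research HFO Method: "In this study we will compare the two groups of patients to see what works best".
- Hypothesis: using HFO data "will result in improved postoperative seizure outcome than the traditional approach".
- Objective (primary): whether adding HFO data "will lead to improved post-surgical seizure outcome 1 year after surgery".

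The SAP takes post-surgery seizure-free time as the primary comparison and states: "The primary analysis will be a log-rank test". It continues: "The secondary analysis of the primary endpoint will be a Cox-proportional hazards regression with seizure-free survival time as the outcome". The analysis is by intention to treat, with a secondary analysis by treatment received. Neither document gives a non-inferiority or equivalence hypothesis, a margin, or a confidence-interval rule for concluding that the arms are equal. The SAP does not state the significance level or whether the test is one- or two-sided.

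**The concern.** Taken literally, the Introduction's aim can be met in two ways: the HFO arm does better, or it does as well. Only the first has a test. A log-rank test assesses a difference between two curves, and failing to find one does not show that the curves agree. Showing that they agree to within a tolerable amount needs a margin and an interval lying inside it, and the plan has neither.

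The worry is about reporting. With 30 subjects a non-significant result is likely under most plausible truths, including some in which the HFO strategy is worse. A reader holding the Introduction's wording might count that result as success. The protocol says the results may change surgical practice, and under Potential Risks it names unexpected neurologic deficit as an added risk of the HFO method. An unsupported claim of equality would therefore not be harmless.

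**Working it through.** **Step 1. Compare the statements.**

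| Place | Direction stated | Role |
|---|---|---|
| Protocol, Introduction | equal or better, plus feasibility | narrative aim |
| Protocol, New Research HFO Method | which approach works best | narrative |
| Protocol, Hypothesis | improved | labelled hypothesis |
| Protocol, Objective | improved at 1 year | labelled primary objective |
| SAP | comparison of seizure-free time, log-rank | primary analysis |

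Equal appears once, in a sentence that also covers feasibility. The labelled hypothesis, the labelled objective and the test are consistent with one another. The log-rank test is not confined to improvement: in its usual two-sided form it responds to a difference in either direction, so a detectably worse HFO arm would show.

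**Step 2. What changes if the word is removed?** The endpoint, test, Cox model, analysis sets and number of subjects all stay as they are. The 30 subjects are stated without alpha, power, effect size or margin, so there is no design calculation to reproduce and none that depends on the word.

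**Step 3. Could this trial have been meant as a non-inferiority trial?** Inputs from the protocol: 30 subjects (Number of Subjects), 1:1 allocation (Randomization), hence 15 per arm, and a seizure-free rate of about 65% (Background and Rationale, with no time point). Assumptions of mine: 65% is the 12-month rate in both arms, one-sided alpha 0.025, 80% power, no dropout.

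Standard error of the difference = √(2 × 0.65 × 0.35 / 15) = 0.174.

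n per arm = (1.960 + 0.842)² × 2 × 0.65 × 0.35 / margin². Power at 15 per arm = Φ(margin / 0.174 − 1.960).

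| Margin (points) | n per arm for 80% power | Power at 15 per arm |
|---|---|---|
| 10 | 358 | 8% |
| 15 | 159 | 14% |
| 20 | 90 | 21% |
| 30 | 40 | 41% |

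The smallest margin with 80% power at 15 per arm is (1.960 + 0.842) × 0.174 = 0.49, or 49 points. This size suits no ordinary non-inferiority claim, which supports reading equal as loose wording rather than as a second hypothesis left without its analysis.

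**Step 4. How little would a null result show?** The 95% half-width with 65% in both arms is 1.960 × 0.174 = 0.34, or 34 points.

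I also considered simulated log-rank tests with 15 per arm. Follow-up ends at 12 months, as the protocol states: "However, will be following the subject for epilepsy outcome up to 12 months after surgery". Further assumptions are exponential times, a two-sided 5% test, no dropout and control rates of 55/65/75%. The percentage of trials that are non-significant is:

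| True deficit in HFO arm | 55% | 65% | 75% |
|---|---|---|---|
| none | 95.0 | 95.0 | 95.0 |
| 10 points | 91.2 | 91.2 | 90.9 |
| 20 points | 79.3 | 79.8 | 79.0 |
| 30 points | 57.4 | 60.4 | 59.7 |
| 40 points | 28.5 | 35.4 | 36.9 |

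These cells come from 100,000 runs each. A separate rerun of 20,000 per cell agreed to within 0.6 points. A null result therefore cannot be read as equality. A very large deficit, though, would usually be detected.

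**Step 5. Where do these figures come from?** They depend on 15 per arm and the assumed rates. Replace equal or better with better and every figure in steps 3 and 4 is the same.

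**The case for a change.** The strongest case for a change is that the sentence is worded as the aim of the study, not as background, and that correcting it costs one phrase. One further SAP sentence, saying that a non-significant result is not evidence of equality, would close off a misreading that is easy to make at this sample size.

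Part of this stands. The wording is inconsistent, and an editor revising the protocol for other reasons could align it with the Hypothesis. The rest does not amount to a fault in the plan. The misreading is one that a future author would have to commit; nothing in either document sets it up as a decision rule. That non-significance does not establish equality is a general principle of interpretation, and many sound SAPs leave it unwritten.

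A larger remedy, adding a 12-month interval for the difference and an unadjusted Cox model, goes further than the mismatch requires. The SAP's Cox model already includes treatment ("Covariates will be treatment, and subject-level characteristics (ex. age and gender"), so an estimate of the treatment effect is planned. An interval on raw 12-month counts would also need a rule for subjects lost before 12 months, a problem the log-rank test does not have in that form because it censors them.

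**Conclusion.** The inconsistency is genuine but clerical. The labelled hypothesis, the primary objective and the primary test all fit a superiority comparison, and an analyst following them would reach a sound conclusion without reference to the Introduction. Rewording the phrase would change no test, endpoint or figure, so no change to the plan follows.

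The figures given, an interval of about ±34 points and roughly 79–80% non-significance under a 20-point deficit, rest on the assumed two-sided 5% level, 12-month control rates of 65% and 55–75% respectively, exponential times and no dropout. They show why a null result from this trial must not be called equality. They measure the consequence of enrolling 30 subjects, which is a separate matter from this wording.

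### The primary objective is seizure outcome at 1 year, but the SAP's primary analysis of seizure-free time has no event definition or 12-month horizon, and no analysis estimates the 1-year outcome

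*Protocol*

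**What the plan says.** **Protocol.** The Objective section sets the primary question as whether HFO data added to ECoG data "will lead to improved post-surgical seizure outcome 1 year after surgery". No scale, responder definition or definition of seizure freedom follows. Under Length of Study Visits, the study "will be following the subject for epilepsy outcome up to 12 months after surgery", and the last visit in the schedule of events is at 12 months.

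**SAP.** The primary comparison is the "comparison of post-surgery seizure free-time between the SOC and SOC+HFO study arms". On the test, the SAP says "The primary analysis will be a log-rank test". The same endpoint is then analysed by "Cox-proportional hazards regression with seizure-free survival time as the outcome". The SAP does not define the event, say when counting starts, or give a censoring time, and it mentions neither 1 year nor 12 months. The one seizure outcome at a fixed time is secondary: "Secondary outcomes of 2-year seizure-free rate will be assessed with logistic regression models".

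**The concern.** The objective names a time point; the primary analysis compares whole curves of unspecified length. A log-rank test gives a p-value and the Cox model a hazard ratio. Neither is the proportion of children seizure-free at 1 year in each arm, or the difference between those proportions. The logistic model would give something closer to that, but at 2 years, when no visit is scheduled.

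Two things are at stake. First, the trial could finish without an estimate for its own primary question. Second, seizure-free time and 1-year outcome may classify the same subject differently. With 30 subjects, a few such cases can change the result.

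**Working it through.** The plan gives no figure to reproduce on this point. The sample size of 30 comes without alpha, power, effect size or number of events. The check is therefore a comparison of the texts, followed by an illustration.

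**1. The two documents side by side**

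| Element | Protocol | SAP |
|---|---|---|
| Primary quantity | Seizure outcome | Seizure-free time |
| Time point or horizon | 1 year | None stated |
| Event and time origin | Not defined | Not defined |
| Fixed-time seizure analysis | 1 year implied by the objective | 2 years only |
| Follow-up available | Up to 12 months | Not stated; the 2-year rate needs 24 months |

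Nothing in either document links the two primary quantities. Time to first seizure is the natural reading of seizure-free survival time under log-rank and Cox methods, but it is an inference.

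**2. Two readings of the 1-year outcome**

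- *Status at 12 months.* A subject with an early transient seizure who is then seizure-free is an event in the SAP and a success for the objective.
- *Continuous freedom from surgery to 12 months.* The event is the same in both documents. What is missing is the 12-month cut-off and the 12-month estimate.

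**3. Size under the status reading**

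Inputs: 65% seizure-free (Background and Rationale; the time point is not stated there, so 12 months is assumed) and 30 subjects. Let q be the share of those seizure-free at 1 year who had an early seizure that then stopped (assumed; the documents give no rate).

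Event-free through 1 year = 0.65 × (1 − q). Extra failures = 30 × 0.65 × q.

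| q | Event-free through 1 year | Extra failures among 30 |
|---|---|---|
| 5% | 0.65 × 0.95 = 61.7% | 0.98 |
| 10% | 0.65 × 0.90 = 58.5% | 1.95 |
| 20% | 0.65 × 0.80 = 52.0% | 3.9 |

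**4. Effect on power under the status reading**

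Simulation of 8,000 runs with 15 per arm, two-sided 5% (assumed) and exponential times. Seizure-free rates at 12 months are 65% v 90% (the 90% is assumed). Transient seizures in the first week are added to the same share of both arms, and the log-rank test is censored at 12 months.

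| Transient share, both arms | Log-rank | Fisher on 12-month status | Pearson on 12-month status |
|---|---|---|---|
| 0% | 38% | about 23% | about 39% |
| 10% | 24% | about 23% | about 39% |
| 20% | 17% | about 23% | about 39% |

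**5. The reverse case**

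Take equal 12-month status (65% in both arms), with transient early seizures in 20% v 0% of the subjects seizure-free at 1 year (assumed). The log-rank test rejected in 14% of runs; on 12-month status, Pearson rejected in 5% and Fisher in about 2%. The two quantities can therefore give different answers from the same trial.

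**The case against.** The strongest reply is that the protocol already supplies the horizon. Follow-up stops at 12 months, so data gathered under it are censored there, and a log-rank test on them does analyse the first year's seizure experience. The background section also frames surgical success as postoperative seizure freedom, which fits continuous freedom and makes the event identical. Much of this stands, and it is why the early-seizure example holds only conditionally. But the SAP does not state the cut-off, its 2-year outcome presumes longer observation, and a log-rank test yields no 12-month estimate even with the cut-off in place.

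Three stronger readings are tempting, and the documents do not support them:

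- *A reader might infer that a first seizure late in the year counts as near success in the log-rank test.* It does not. With 7 events among 30 subjects and no earlier censoring, the first event scores 1 − 1/30 = +0.97. The last scores 1 − (1/30 + 1/29 + … + 1/24) = +0.74, and a subject censored at 12 months scores −0.26. The last event lies (0.74 + 0.26)/(0.97 + 0.26) = 81% of the way from success to earliest failure.
- *A reader might infer that the primary result could be chosen after seeing the data.* The SAP names the log-rank test as primary, so this is weak.
- *A reader might infer that a 12-month status test is simply more powerful.* That depends on the test. The only categorical test the SAP names is Fisher's exact, for complications. Against Fisher, the log-rank test is clearly better with no transient seizures, about equal at 10% and worse at 20%.

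**Conclusion.** The concern holds as a mismatch between the current texts: a 1-year primary objective, a primary analysis with no stated event or horizon, and a sole fixed-time seizure outcome at 2 years. That the plan contains no 1-year estimate follows from the text alone and needs no numerical assumption.

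That the primary test misclassifies subjects who meet the objective is conditional. It applies only if the 1-year outcome means status at 12 months, and its size rests on assumed transient-seizure rates. On the continuous-freedom reading, that part falls away. The change should be made because it affects what the trial can conclude and costs little, but the log-rank test is not itself a wrong choice.

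**What to change.** Name one primary endpoint in both documents.

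- **SAP, primary analysis:** keep the log-rank test. Define the event as first seizure, counted from surgery, and censor every subject at 12 months.
- **Protocol, Objective:** reword the primary objective as seizure-free time over the first 12 months.
- **SAP, primary estimate:** report the difference between arms in 12-month Kaplan-Meier seizure-free proportions with its 95% CI.
- **SAP, first secondary outcome:** replace the 2-year rate with seizure status at the 12-month visit, and state how status is defined.

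The Kaplan-Meier difference then answers the continuous-freedom reading and the status analysis answers the other.

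The cost is wording in both documents and one added analysis. No new data are needed, because a 12-month visit with questionnaires on seizure frequency is already scheduled. Any seizure information after month 12 is lost to the primary test. Keeping the log-rank test does not remove the power loss shown above: the simulated test was already censored at 12 months, so early transient seizures would still count as events.
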